### ***Focus groups***

Two discussion groups with all PE teachers will be held throughout the study (See Figure 1). Firstly, one focus group will be done immediately after the end of the fourth session of the training program. The main themes covered in the focus groups will be (1) the content of each session of the program (i.e., theoretical background, design of motivational strategies in different teaching units, and implementation of different PE lessons), (2) the didactical approach (e.g., images, videos, practical examples, formative assessment, and interactive exercises) and their perception of (de)motivating teaching style from de trainers (i.e., congruent teaching), (3) perceived changes in beliefs about (de)motivating teachers styles, the satisfaction of their basic psychological needs, and (de)motivating teaching styles towards students, and (4) overall assessment of the training (e.g., innovation, practical usefulness, feasibility of the motivating strategies, intention to implement the motivating strategies, satisfaction, etc.). This last question will complement the short questionnaire completed by the PE teachers at the end of each training program session (see above).

The second focus group will take place at the end of the intervention, coinciding with the completion of the teachers' and students' questionnaires in the post-test (T3). This will make it possible to find out the teachers' perception of the implementation phase, as well as of the different study variables. The main themes covered in the focus groups will be (1) the follow-up of the training program (e.g., individual and group sessions), (2) perceived changes in beliefs about (de)motivating teachers' styles, satisfaction of their basic psychological needs, (de)motivating teaching styles towards students, and job satisfaction, emotional exhaustion, and job performance.

Both focus group will be facilitated by a female with expertise in PE teaching instruction, the SDT framework, and qualitative methodology. To encourage open communication among PE teachers, the trainers will not be present during the group discussions. Focus group sessions will be started with an overview of both the aim and the procedure. The moderator will be supported by a co-moderator, tasked with managing logistics, recording notes, and overseeing the recording equipment. Furthermore, to conclude the focus group, the co-moderator will provide a summary of the primary viewpoints and will ask PE teachers whether these perceptions accurately reflect their views or if they wish to contribute additional insights.

Focus groups will take place in an empty, comfortable, and neutral room, lasting approximately 50 minutes. All sessions will be videotaped and transcribed to draw conclusions from the discussions.

### ***Teachers' Training Program and Intervention Implementation Towards Students***

The intervention will comprise two phases in the experimental group: 1) a teacher-training phase (four face-to-face sessions and two follow-up sessions) and 2) an implementation phase where teachers will implement the strategies to the students (see Figure 1).

#### ***Teachers' Training Program in the Experimental Group***

The first part of the training program will last four weeks and eight hours in total. All PE teachers will participate in four weekly face-to-face group sessions, each two hours long, scheduled from 17:00 to 19:00. Grounded in the circumplex model, the sessions will aim to increase autonomy support and structure, while reducing controlling and chaotic approaches towards students. The training will be delivered by two members of the research team experienced in SDT-training programs for PE teachers.

The program incorporates strategies from established SDT-based teacher training programs (Aelterman et al., 2013; Cheon et al., 2020; Reeve et al., 2022; Reeve & Cheon, 2021). For example, to lead by example (i.e., congruent teaching), trainers provided autonomy support and structure and avoided control and chaos during all sessions of the training program. It is worth noting that the pre-test values on teachers' and students' perceptions of teaching approaches will allow the design of the training program to be individualized to the needs of the participants, particularly in the individual follow-up session.

The first two-hour face-to-face training session will unfold in a hybrid theoretical-practical workshop format. It will commence with an introductory presentation by the trainers, followed by a brief review of the objectives and contents of the training program. The session will then transition into an autonomy-supportive exercise, where PE teachers will select a “getting-to-know-you” activity (15 min). Teachers should individually identify on a green sticky note some teaching behaviours of a good PE teacher they have had (e.g., “he/she allowed us to choose some tasks”) and on a red sheet those of a bad PE teacher (e.g., “he/she constantly punished us”). Afterwards, once these sticky notes have been stuck on the board, teachers will have the opportunity to read and explain their experiences to the rest of the group (15 min). This activity will be linked to the theoretical background (i.e., SDT and circumplex model) that will be used throughout this training program. Thus, through ongoing collaboration and involvement of PE teachers (e.g., “What do you think the need for competence refers to?”), a concise overview of the SDT framework and circumplex model will be provided. This will be done using real-life examples and personal anecdotes shared by both the trainers and the teachers themselves (30 min). Finally, teachers will be encouraged to individually design a series of generic strategies to support autonomy and

provide structure, as well as to be less controlling and chaotic towards students in PE lessons (15 min). They will share these strategies with another teacher (15 min) and, finally, in pairs, with the entire group and trainers. This will lead to a collective reflection on the strategies themselves (e.g., “Why do you think this strategy might satisfy the need for autonomy?”, “Could it satisfy or frustrate some other basic psychological need?”) (25 min). At the end of the session, a brief explanation of the next steps and the objectives for upcoming sessions will be given to foster a positive disposition among the teachers. They will also be asked about the teaching units in their annual teaching plans that they still have to teach in each of the classroom groups involved in the study (5 min).

The second two-hour face-to-face training session will involve the design of motivational strategies in a practical workshop. In the first part of this session, a brief review of the previous session will be made, recalling theoretical background, identifying (de)motivating teaching behaviours, and reviewing the implementation in their PE lessons of the strategies proposed by PE teachers in the last session. For this, teachers will actively engage in the explanation process to assess the acquired learning (15 min). Afterwards, some videos of (de)motivating teaching strategies implemented by other secondary PE teachers will be shown. The videos will be selected based on teaching behaviours that have not been detailed by PE teachers in the previous training session (e.g., autonomy support; “provide an explanatory rationale”). Teachers will need to identify (de)motivating teaching behaviours depicted in the videos and consider their potential consequences on students’ basic psychological needs satisfaction or frustration (25 min). Subsequently, the teaching units mentioned by the PE teachers in the previous training session will be listed. At least two of these teaching units will be chosen among all of them to design motivational strategies for small working groups (30 min). A coordinator of each group will present the different (de)motivating teaching strategies of the teaching unit and trainers and the rest of the teachers

will conduct a formative assessment of the co-created strategies (30 min). Finally, one teacher from each group will be offered the opportunity to teach one of the lessons of these teaching units to his/her colleagues, integrating at least two strategies from each (de)motivating teaching behaviour. The other teachers in the group will undertake to assist the volunteer teacher in designing the class.

The third two-hour face-to-face training session will involve applying and receiving the strategies learned throughout the training program in a simulated real-life situation (i.e., PE lesson) with the other participating teachers and other volunteers. One teacher from each group will teach one of the lessons of these teaching units using (de)motivating teaching behaviours (45 min per teacher). Afterwards, the trainers and the other PE teachers provided a formative assessment of positive strengths and areas for improvement (15 min after each class). Finally, another teacher will be encouraged to implement a lesson from the teaching unit of his or her annual teaching plan, with the help of the research team via Google Meet, in the last session of the training program.

The fourth face-to-face training session will focus on continuing the practical application of (de)motivating teaching strategies in a simulated real-life situation. This last session will be intended to be an example for the rest of the teachers in which a wide variety of (de)motivating teaching strategies appeared frequently. This last session will follow the same procedure as the previous class (45 min of class and 15 min of reflection). In the second part of the class, a final in-depth reflection on the first part of the training program will take place, focusing on synthesizing all the key concepts covered in the initial phase of the training program across the four sessions. Finally, teachers will receive a dossier of (de)motivating teaching behaviours organized in styles and approaches in line with the motivational behaviour change techniques (MBCTs) identified by themselves and the trainers in the training (see in the section on intervention implementation). Finally, the possibility of

creating a WhatsApp group will be offered to facilitate the follow-up of the training program. Teachers will be able to share their progress, ask questions about the implementation of strategies, etc.

During the implementation phase, there will be one individual and one group follow-up sessions of the training program (see Figure 1) to monitor the implementation of strategies, give feedback on positive aspects and areas for improvement, and identify potential barriers or challenges encountered in the implementation of motivational strategies during this period. For the first follow-up session, the individual one, the trainers will visit each school to observe one PE class by each teacher. Subsequently, a detailed report of their teaching performance will be provided. The report will include: 1) a series of motivational strategies that the teacher used in their class, 2) a proposal of motivational strategies that the teacher could have used in their class, 3) a report of their teaching profile based on the pre-test questionnaire values, including both the teachers' self-perception and the students' perceptions, and 4) advice and motivational strategies to improve their teaching profile in that specific class. For the second follow-up session, the group session, the objective will be to analyze the videos (taken from the first observational measure) of each teacher. The trainers will thoroughly review each video to extract clips showing each teacher using motivating and/or demotivating strategies. After each strategy is presented, a brief discussion will be held with the other teachers to identify strengths and possible improvement suggestions for these strategies. These follow-up sessions will be individualized and adapted to the needs of each teacher.

**Table 1.** *Summary of the program training sessions.*

Face-to-face session 1	Face-to-face session 2	Face-to-face session 3	Face-to-face session 4	Follow-up session 1	Follow-up session 2
The entire group of PE teachers	Individual	The entire group of PE teachers			

1. Presentation and getting-to-know-you activity	1. Summary of the previous lesson	1. Application of the motivational strategies in two PE lessons of a simulated real-life situation and subsequent reflection.	1. Application of the motivational strategies in one PE lesson of a simulated real-life situation and subsequent reflection.	1. Observation of the PE teachers' real classes and subsequent constructive feedback.	1. Observation of the PE teachers' real classes and subsequent constructive feedback.
2. Teaching behaviours of good/bad teachers.	2. Identifying (de)motivating teaching behaviours with real videos.			2. Summary of the key points of the four previous sessions	
3. Explanation of the theoretical backgrounds.	3. Design of specific motivational strategies in different teaching units				
4. Design of motivational strategies in PE lessons.					

## **Intervention Implementation Towards Students in the Experimental Group**

It should be noted that, although teachers will begin to apply some of the (de)motivating teaching styles and approaches from the first day they attend the training program, they will be implemented with greater variety, frequency, and intensity after the first part of the training (first four face-to-face sessions). The implementation phase will therefore last approximately five months, from January to the end of May. The training program that will be received by PE teachers will be focused on the motivational strategies proposed by Ahmadi et al. (2023). Teachers will be encouraged to implement as many MBCTs as possible in variety, frequency, and intensity in each of their PE classes.

### **Control group**

Control group teachers will not initially receive the training program and, as a result, will not intentionally implement any motivational strategy. They will only complete the questionnaires at the same times as experimental group teachers (See Figure 1). Control group teachers will receive the training program after the last study measurement, as well as an extensive final report on their teaching profile, and a series of motivational strategies aimed at enhancing their (de)motivating teaching style.

### ***Analysis plan***

#### ***Quantitative analyses***

Firstly, the effects of the four sessions of the training program on the study variables assessed in teachers will be examined. The overall mean for each of the 11 variables perceived by PE teachers about the quality of the training program (e.g., interaction, innovation, interest, intelligibility, etc.) will also be calculated, representing the mean across the different sessions. A repeated measures analyses of variance (ANOVA) will be used to assess PE teachers' global appreciation of 11 variables related to the quality of the training program (e.g., interaction, innovation, interest, intelligibility, etc.) across the sessions of the training (i.e. within-subject analyses). Accordingly, each of the training sessions will be introduced as an independent variable (i.e. within-subject factor) and repeated measures of the PE teachers-related variables will be entered sequentially as dependent variables.

Secondly, the effects of the intervention implementation in PE lessons on study variables for both teachers and students will also be examined. Levene and Kolmogorov–Smirnov tests will be used to ensure the equality of variances and normal data distribution, respectively ( $p > .05$ ). Cronbach's coefficient will be calculated for each study variable across the three measurements. To examine the effects of the intervention on study variables, a  $3 \times 2$  (time x condition) repeated measures multivariate analysis of covariance (MANCOVA) will be performed for both teachers and students. Age, gender, teaching experience, type of school (public or private), and school location (rural or urban) will be introduced as covariates among teachers, while age, gender, and school grade level will be introduced as covariates among students. Subsequently, to examine intragender differences of the intervention on study variables, a  $3 \times 2 \times 2$  (time x condition x gender) repeated measures MANCOVA will be performed for both teachers and students. The same covariates will be entered as previously analysis, excluding gender. Multiple paired t-tests with Bonferroni correction will be calculated to determine between-group (i.e., experimental-control group) and within-group (i.e., pre-post) differences. Cohen's criteria will be used as indicators of small (.01), moderate

(.06), and large (.14) effect sizes (Field, 2017). All statistical analyses will be conducted using IBM SPSS Statistics v.25.0. Finally, a longitudinal structural equation model will be used to analyze the predictive relationships between the study variables, allowing for observation of potential differences at the three specific times (i.e., pre-test, middle, and post-test) when data are collected.

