## **Materials and methods**

### ***Context, design, and randomization***

[figure not shown]
This study will be carried out in a northeast region of Spain [details masked for review process]. PE is mandatory for every secondary school student in Spain. Each student receives two 50-minute coeducational PE lessons per week. Spanish Secondary PE teachers are expected to teach between 18 and 21 hours per week. Typically, the annual teaching plan of PE teachers includes approximately six to eight distinct teaching units per year. These units encompass various content types such as individual, cooperative, and interactive sports and games, as well as body expression, health-related fitness, and outdoor activities, all of which are outlined in the PE curriculum. The academic year lasts from September to June, divided into three terms, each separated by a holiday period (i.e., Christmas and Easter).

A randomized controlled trial design with a mixed-method approach will be carried out. PE teachers agreeing to participate in the trial will be randomly assigned to either the experimental or the control group. Randomization will be conducted using the digital tool available at <https://echaloasuerte.com/>. To prevent contamination of the experimental condition, schools will only participate in one group (i.e., experimental or control). Subsequently, at least two groups of students from each PE teacher will be randomly selected.

This study will comprise two phases: 1) a teacher-training phase and 2) an implementation phase with students. It should be noted that the training program will continue with some individual and group sessions during the implementation phase. Since teachers' and students' perceptions of (de)motivating teaching styles and approaches and other study variables require several months for greater accuracy in their perceptions, the

training program will not start until the second term of the academic year (for more details see Figure 1).

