### **Sample size calculation**

The sample size for this intervention-based study was calculated using R Studio to ensure adequate power in the detection of potential statistically significant effects.

Considering a multi-level design nesting center, PE teacher and group, the sample size calculation was grounded on an anticipated effect size of 0.5, reflecting a moderate impact of the intervention. The power of the study was set at 80% with a significance level (alpha) of 0.05, aligning with common practices in educational research (McConnell et al., 2019).

Acknowledging the inherent structure of this study, an Intra-Class Correlation (ICC) of 0.1 was assumed based on similar educational settings (Hedges & Hedberg, 2007). This ICC estimate accounted for the expected homogeneity within the three levels (class group within PE teacher, PE teacher within center). To accommodate potential participant dropout, particularly among students, we incorporated a 40% anticipated dropout rate into our calculations (e.g., Meerits et al., 2022). The minimum sample size was adjusted to 210 students across 15 PE teachers, averaging 14 students per teacher. This adjustment ensures that our study maintains sufficient statistical power even in the face of anticipated losses, thereby safeguarding the integrity and validity of our findings.

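### Student outcomes are analysed as if students were independent, although teachers are randomised and an ICC of 0.1 is assumed

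*Protocol*

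**What the plan says.** **Design** (Protocol, Context, design, and randomization). The randomised unit is the teacher: "PE teachers agreeing to participate in the trial will be randomly assigned to either the experimental or the control group". Against contamination, "schools will only participate in one group (i.e., experimental or control"). Then "at least two groups of students from each PE teacher will be randomly selected". Participants and recruitment expects at least 16 teachers (eight per arm), caps them at 20, and asks for at least two classes of at least 14 students per teacher.

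**Sample size** (Sample size calculation). "Considering a multi-level design nesting center, PE teacher and group, the sample size calculation was grounded on an anticipated effect size of 0.5", with alpha 0.05, 80% power and an ICC of 0.1. On the ICC: "This ICC estimate accounted for the expected homogeneity within the three levels (class group within PE teacher, PE teacher within center"). On losses: "we incorporated a 40% anticipated dropout rate into our calculations". The result: "The minimum sample size was adjusted to 210 students across 15 PE teachers, averaging 14 students per teacher".

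**Analysis** (Quantitative analyses). For time x condition, a "repeated measures multivariate analysis of covariance (MANCOVA) will be performed for both teachers and students", then a version that adds gender as a factor. Student covariates are age, gender and school grade (gender is dropped from the covariates in the second model). Bonferroni-corrected t-tests, all described as paired, cover both between-arm and pre-post differences. A longitudinal structural equation model closes the section. None of these has a random effect, a robust variance or a cluster summary for class, teacher or school.

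**The concern.** The sample size section describes students nested in classes, teachers and centres; the analysis section tests them as independent observations. Both cannot be right for the same data. Clustering is built into this trial, because all students of a class rate the same teacher.

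This is not a detail that an SAP would fill in. The Protocol names a specific method, and that method does not fit its design.

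Two kinds of test must be kept apart:

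- **Between-arm comparison at one time point.** Students of one teacher share part of the outcome variance, so the student-level standard error is too small, whether that variance sits at teacher or class level.
- **Time x condition.** Cluster effects that stay constant cancel from within-student change. Only cluster-specific drift between T1 and T3 harms this test. Drift is plausible here: the implementation runs about five months and the follow-up feedback is individualised by teacher.

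At stake is H3, the claim that students benefit. It rests on these tests, with only 16-20 randomised units behind them.

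A wording point: *paired* fits pre-post contrasts but not a comparison of independent arms.

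**Working it through.** **1. The plan's own figure.** Two-sided alpha is assumed, since sidedness is not stated. Per arm, n = 2(1.96 + 0.8416)²/0.5² = 62.8, so 63; total 126; 126/0.6 = 210. This matches the stated 210 exactly, with no design effect. The ICC is described but does not enter this calculation. With 14 students per teacher it would give 126 x 2.30 = 290 evaluable students and 483 before dropout.

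**2. Between-arm test at one time point.** Inputs: ICC 0.1; m students per teacher. The Protocol gives 14, or 2 x 14 = 28 if both classes count in full; after 40% dropout these become 8.4 and 16.8. The level of the ICC is not stated, so three splits are shown, with two equal classes per teacher assumed. With total variance 1 and rho_T + rho_C = 0.1:

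- DE = 0.9 + m·rho_T + (m/2)·rho_C
- true size = 2[1 − Φ(1.96/√DE)]

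| ICC located at | m = 8.4 | m = 14 | m = 16.8 | m = 28 |
|---|---|---|---|---|
| Teacher: DE | 1.74 | 2.30 | 2.58 | 3.70 |
| Teacher: size | 13.7% | 19.6% | 22.2% | 30.8% |
| Half and half: DE | 1.53 | 1.95 | 2.16 | 3.00 |
| Half and half: size | 11.3% | 16.0% | 18.2% | 25.8% |
| Class: DE | 1.32 | 1.60 | 1.74 | 2.30 |
| Class: size | 8.8% | 12.1% | 13.7% | 19.6% |

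Null simulation (10,000 trials, 16 teachers, m = 8, 14, 16, 28) agrees: 13.7, 19.8, 21.4, 31.8% at teacher level; 8.8, 12.1, 13.2, 19.0% at class level. A t-test on teacher means gives 4.6-5.4%.

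With Bonferroni for an assumed three comparisons (nominal 0.05/3 = 1.7%), the true size is 7.0-21.3% (teacher) or 3.7-11.4% (class). Any clustering removed by adjusting for grade is not counted.

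**3. Time x condition (illustrative).** Let g be the ICC of the change scores. It is not the Protocol's ICC, and its values here are assumed. For one outcome and a 2-df test in large samples, size = 0.05^(1/DE), where DE = (1 − g) + m·g for drift at teacher level or (1 − g) + (m/2)·g at class level. For example, g = 0.02 and m = 8 at teacher level give DE = 1.14 and size 7.2%. At g = 0 the size is 5%. Simulation (20,000 trials, 16 teachers):

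| g, level of drift | m = 8 | m = 16 | m = 28 |
|---|---|---|---|
| 0.02, teacher | 6.8% | 10.0% | 14.5% |
| 0.02, class | 6.1% | 7.1% | 9.1% |
| 0.05, teacher | 11.0% | 18.1% | 28.2% |
| 0.05, class | 7.3% | 10.9% | 16.6% |

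The same test on teacher means stays at 4.7-5.3%.

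A second parameterisation holds the ICC at 0.1 and varies its correlation over time, assuming a within-student correlation of 0.5. Over 15 teachers x 14, 16 x 17 and 16 x 28 students, it gives about 5% at cluster autocorrelation 1, 14-25% at 0.8 and 27-45% at 0.5. The direction is the same; the size depends on the assumption.

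**4. Power once clusters are respected.** d = 0.5, one time point; variance of a teacher mean = rho_T + rho_C/2 + 0.9/m; noncentral t with df = teachers − 2. The last column multiplies the variance by 1 − 0.5² (assumed T1-T3 correlation of teacher means 0.5), with df = teachers − 3.

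| Teachers x students | ICC at teacher | ICC at class | Teacher, baseline-adjusted |
|---|---|---|---|
| 15 x 8.4 | 50% | 62% | 62% |
| 16 x 8.4 | 53% | 65% | 65% |
| 16 x 16.8 | 66% | 82% | 78% |
| 16 x 28 | 73% | 90% | 84% |

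**The case against.** The strongest reply is that the 14-31% figures do not describe the leading test. The MANCOVA comes first, and its time x condition term holds 5% under constant cluster effects. If the between-arm t-test counted only after a significant interaction, the two together would reject in just 1.0-1.7% of null trials (simulated with a constant teacher-level ICC of 0.1, a within-student correlation of 0.5 and 8 to 28 students per teacher). This would matter if the plan stated such gating. It does not, and gating would not protect the interaction itself against drift.

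The drift figures have no source in the Protocol and are univariate, whereas the planned test is multivariate. Both points stand: the figures must not be read as the error rate of the planned MANCOVA. That does not rescue the plan. With 4-15 independent outcomes (an assumption) and g = 0.02, the multivariate test rejected in 8-53% of null trials.

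A school level may be largely redundant, since the Limitations section says that training will not target teachers of the same school. This is fair, and it is why school is needed only where a school supplies more than one teacher.

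Finally, replacing only the MANCOVA and the between-arm tests leaves the pre-post tests exposed to the same drift. This also stands. With DE = (1 − g) + m·g and the one-df formula of step 2, g = 0.02 and m = 8 give DE 1.14 and size 7%; g = 0.05 and m = 28 give DE 2.35 and size 20%. The structural equation model names no cluster structure either. Both are reasons to widen the fix.

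**Conclusion.** The concern holds, and the plan must be changed. The student analysis named in the Protocol contradicts the Protocol's own randomisation and its description of nesting.

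- **Between-arm tests at one time point:** anti-conservative in all twelve settings examined, at 9-31% against a nominal 5%. This rests on the stated ICC of 0.1, 8.4 to 28 students per teacher, two equal classes per teacher for the class-level part, and tests that are not gated.
- **Time x condition:** valid only if cluster effects are constant over time. Otherwise it is inflated, by an amount that the Protocol's figures cannot fix.

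The power figures are not the trial's true power. They show only that the stated 80% cannot be carried over to a valid analysis without rechecking.

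**What to change.** In Quantitative analyses, replace the student MANCOVA and the between-arm t-tests as follows.

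1. **Main model.** One linear mixed model per student outcome, with time, condition, time x condition (and the interaction with gender for the gender question) and the listed covariates. Random effects for student, class, teacher and teacher x time; school as the top level where a school contributes more than one teacher.
2. **Small-sample inference.** Kenward-Roger or Satterthwaite degrees of freedom that reflect the randomised clusters. Confirm that the named software version offers the chosen method.
3. **Fallback, stated in advance.** If the model is singular or does not converge with 16-20 teachers, analyse mean changes per teacher (or per school). This alone is enough to hold the level.
4. **Contrasts.** Take the between-arm contrasts at T2 and T3 from this analysis with the planned Bonferroni correction, and state the number of comparisons. Keep *paired* for within-group contrasts only, and preferably take these from the same model so that they allow for drift.
5. **Structural equation model.** State how it handles clustering.

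The cost is wording; no new data are needed. Confidence intervals widen, the omnibus test across outcomes is lost, and the sample size must be recalculated for the analysis that will be used.
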